### 6.4.1 Analysis of Primary Efficacy Endpoints

For Phase 2, the primary efficacy endpoint will be CRc rate for subjects with R/R AML and (CR+ BM CR +PR) rate for subjects with R/R higher risk MDS.

- AML
  - CRc rate is defined for AML subjects as the number of subjects who achieve the best response of CRc (CR, CRp or CRi) divided by the number of subjects in the analysis population.
  - Response to treatment will be defined per Cheson et al., 2003
  - Response rates will be calculated and their 2-sided 90% confidence intervals will be constructed by Clopper-Pearson method by dose level for phase 1 and by dose level and disease type for phase 2.
- MDS
  - CR + BM CR + PR rate is defined for MDS subjects as the number of subjects who achieve the best response of CR or BM CR plus the number of subjects who achieve the best response of PR divided by the number of subjects in the analysis population.
  - Response to treatment will be defined per Cheson et al., 2006
  - Response rates will be calculated and their 90% confidence interval will be constructed by Clopper-Pearson method by dose level for phase 1 and by dose level and disease type for phase 2.

## 6.4.2 Analysis of Secondary Efficacy Endpoints

### 6.4.2.1 Best Response

The best response rate will be estimated and its 90% confidence interval (CI) will be constructed by dose level and disease type using the Clopper-Pearson method using the RAS.

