#### **4.1 Full Analysis Set**

The full analysis set (FAS) will consist of all subjects who are enrolled and receive at least 1 dose of study treatment. This will be the primary analysis set for efficacy analyses.

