## **4.2 Response Analysis Set**

The response analysis set (RAS) will consist of all subjects who are enrolled and receive at least 1 dose of study treatment and have at least 1 post baseline primary efficacy measurement.

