- Partial Remission (PR): For subjects to be classified as being in PR at a post-baseline visit, they must have bone marrow regenerating normal hematopoietic cells with evidence of peripheral recovery with no (or only a few regenerating) circulating blasts and with a decrease of at least 50% in the percentage of blasts in the bone marrow aspirate with the total marrow blasts between 5% and 25%. A value of less than or equal to 5% blasts is also considered a PR if Auer rods are present. There should be no evidence of extramedullary leukemia.
- Not Evaluable (NE)/No Response (NR): In the situation where no bone marrow assessments are performed or myeloblast value is missing, blast value from peripheral blood is missing or  $\leq 2\%$ , and extramedullary leukemia is missing or not present, the response will be

classified as NE. In any case response cannot be categorized as CR, CRp, CRi, PR or NE, it will be categorized as NR.

A complete response classification schema is presented in [Table 1](#), below.

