### **5.1.5 Secondary Efficacy Endpoint: Best Response Rate**

Best Response Rate is defined as the number of subjects who achieve CRc or PR at any of the postbaseline visits divided by the number of subjects in the analysis population. Best response rate is applicable for AML subjects only.

- Best response for AML subjects is defined as the best measured response to treatment for all visits (in the order of CR, CRp, CRI, PR, NR and NE) postbaseline. Subjects who achieve the best responses of CR, CRp, CRI, or PR will be classified as responders. Subjects who do not achieve at least a best response of PR will be classified as non-responders.
- Best response for MDS subjects is defined as the best measured response to treatment for all visits (in the order of CR, PR, BM CR, HI, SD and PD) post-baseline. Subjects who achieve the best responses of CR, BM CR, or PR will be classified as responders. Subjects who do not achieve at least a best response of PR will be classified as non-responders.

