## 6.4 Analysis of Efficacy

Efficacy analyses will be conducted on the FAS and RAS. The interpretation of results from statistical tests will be based on the FAS. The RAS will be used to assess the robustness of the results from the statistical tests based on the FAS. All randomized subjects will be analyzed according to the treatment to which they are randomized/assigned. Efficacy data from the China cohort will be analyzed separately.

Derived response based on central assessment supplemented by local assessment: response will be derived based on the definitions in Section 7.1.1 using centrally evaluated myeloblast counts from bone marrow aspirate or biopsy assessments whichever is present (if both are present, both must qualify for the criteria) and centrally evaluated hematology results including ANC, platelet count and blast count in peripheral blood. If neither central bone marrow aspirate nor biopsy is available at baseline assessment, then myeloblast counts from locally evaluated bone marrow aspirate/biopsy assessments (if both are present, both must qualify for the criteria) will be used for all timepoints of assessment. Missing hematology results will not be imputed.

Derived response will be considered as primary and investigator reported response will be considered as supportive.

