### 6.4.2.2 Objective Response Rate (ORR)

Objective Response Rate (ORR) is defined for MDS subjects as the number of subjects who achieve CR, BM CR, PR or HI at any of the postbaseline visits divided by the number of subjects in the analysis population. ORR is applicable for MDS subjects only.

The ORR will be estimated and its 90% confidence interval (CI) will be constructed by Clopper-Pearson method by dose level using the RAS.

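### SAP 6.4.2.1 and 6.4.2.2 name only the Response Analysis Set for best response rate and ORR, where the protocol makes the Full Analysis Set primary

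*SAP*

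**What the plan says.** **Protocol.** Section 9.2.1 makes the FAS (all enrolled subjects who received at least one dose) the primary set for efficacy. Section 9.2.2 makes the RAS a sensitivity set for response endpoints. Section 9.4 runs the efficacy analysis on the FAS, and 9.4.2, which covers best response and ORR, makes no exception.

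**SAP, general text.** Section 4.1 says of the FAS: "This will be the primary analysis set for efficacy analyses". Section 4.2 restricts the RAS to treated subjects who "have at least 1 post baseline primary efficacy measurement", and leaves out the protocol's sentence on its sensitivity role. Section 6.4 uses both sets, bases interpretation on the FAS, and adds: "The RAS will be used to assess the robustness of the results from the statistical tests based on the FAS".

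**SAP, endpoint text.** For best response rate (6.4.2.1), the 90% interval "will be constructed by dose level and disease type using the Clopper-Pearson method using the RAS". For ORR (6.4.2.2), it is "constructed by Clopper-Pearson method by dose level using the RAS". Neither section names the FAS.

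**Revision history (SAP section 7).** The version 3.0 entries on efficacy analysis cover the derived response in 6.4, the move of OS, EFS and duration of response to listings, and the removal of time to response. The version 2.0 and 2.1 entries list pages and describe China-cohort and operational changes. No entry mentions an analysis set.

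**The concern.** A programmer would normally follow the endpoint-specific sentence. That yields RAS rates only, so two secondary endpoints lose the estimate the protocol planned.

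The two sets treat failures differently. SAP 5.1.5 defines AML best response as the "best measured response to treatment for all visits (in the order of CR, CRp, CRI, PR, NR and NE) postbaseline", then adds: "Subjects who do not achieve at least a best response of PR will be classified as non-responders". A not-evaluable subject therefore counts as a failure. The not-evaluable rule in SAP 5.1.1 opens "In the situation where no bone marrow assessments are performed or myeloblast value is missing". If the measurement that admits a subject to the RAS is a marrow result, the RAS removes treated AML subjects whom 5.1.5 would count as non-responders. Some such subjects are plausible: the first scheduled post-baseline marrow is at cycle 2 day 1, and the protocol's background describes survival of only weeks after second relapse or failed first salvage.

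Denominators would also be mixed. SAP 6.4.1 names no set for the primary rates, so the FAS default applies there, while best response would sit on the RAS.

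**Working it through.** **1. Does the plan's own figure depend on this?** The protocol states power of about 0.83 in each disease at type I error 0.10. I enumerated the three-stage binomial design exactly (12 + 20 + 20 subjects), using the protocol's boundaries.

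- AML: stop at ≤1/12 or ≤5/32, success at ≥12/52, rates 15% against 30%. Power 0.829, type I error 0.067.
- MDS: stop at ≤0/12 or ≤4/32, success at ≥10/52, rates 12% against 25%. Power 0.835, type I error 0.078.

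The stated power reproduces. These figures concern the primary endpoint and do not change with the set used for the secondary rates.

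**2. Effect on AML best response.** CRc and PR both need marrow, so on the marrow reading a subject without a qualifying measurement cannot be a responder. With x responders among n treated and k excluded:

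- FAS rate = x/n
- RAS rate = x/(n − k) = FAS rate ÷ (1 − k/n)

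For one exclusion the ratio is n/(n − 1): 52/51 = 1.020, 32/31 = 1.032, 12/11 = 1.091.

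**3. Illustration.** The stage sizes 12, 32 and 52 come from protocol 9.4.1.3. The 25% rate and the exclusion counts are my assumptions. The 90% Clopper-Pearson limits are the 5% quantile of Beta(x, n − x + 1) and the 95% quantile of Beta(x + 1, n − x), with the RAS denominator in place of n for the RAS column.

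| Treated | Excluded non-responders | FAS rate (90% CI) | RAS rate (90% CI) |
|---|---|---|---|
| 52 | 1 | 13/52 = 25.0% (15.5–36.8) | 13/51 = 25.5% (15.8–37.4) |
| 52 | 2 | as above | 13/50 = 26.0% (16.1–38.1) |
| 52 | 5 | as above | 13/47 = 27.7% (17.2–40.3) |
| 32 | 1 | 8/32 = 25.0% (13.1–40.6) | 8/31 = 25.8% (13.5–41.8) |
| 12 | 1 | 3/12 = 25.0% (7.2–52.7) | 3/11 = 27.3% (7.9–56.4) |

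Over a wider assumed range, exclusion shares of 10%, 20% and 30% multiply the rate by 1.11, 1.25 and 1.43. Nothing in the documents supports any particular share.

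**4. ORR can move the other way.** Hematologic improvement is judged on blood counts and transfusions. An HI responder without the qualifying measurement would leave both numerator and denominator: 13/52 = 25.0% becomes 12/51 = 23.5% (14.2–35.3). I expect this to be rare.

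**5. Mixed denominators.** Suppose 12 of 52 AML subjects reach CRc, none has PR, and 5 are excluded from the RAS. CRc on the FAS is 12/52 = 23.1% (13.9–34.7). Best response (CRc + PR) on the RAS is 12/47 = 25.5% (15.4–38.1). The difference looks like a PR contribution, but there is none. For MDS, 5.1.5 counts CR, BM CR and PR as response, as the primary endpoint does, and 6.4.2.1 is by disease type. The same responders could therefore appear over two denominators.

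**6. What the size turns on.** SAP 4.2 does not define the qualifying measurement. Protocol 7.1.1.3 links the primary endpoints to hematology tests done at every visit. If hematology alone qualifies, the RAS nearly equals the FAS and the effect is close to zero.

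**The case against.** The strongest reply is that the parent section settles the matter. SAP 6.4 governs 6.4.2 and runs efficacy on both sets, SAP 4.1 keeps the FAS primary, and neither endpoint section says the RAS replaces the FAS. That makes the SAP ambiguous, and a careful programmer might produce both tables. It does not remove the conflict: 6.4.2.1 and 6.4.2.2 still name only the protocol's sensitivity set. The interpretation and robustness sentences in 6.4 also refer to statistical tests, whereas these two sections give estimates with intervals.

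Other points carry some weight:

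- **The not-evaluable rule is narrower than missing marrow.** It also requires peripheral blasts missing or ≤2% and extramedullary leukemia missing or absent; otherwise the subject is NR. A response category can therefore be assigned without marrow, which makes the marrow reading of the RAS less certain. NR is still non-response under 5.1.5, so the FAS handling is the same.
- **Marrow is also scheduled at end of treatment**, which limits exclusions.
- **The revision-history point is modest.** The wording may date from version 1.0, in which case there was nothing to log. The documents do not show when it entered.
- **Little is lost beyond recovery.** SAP 6.2.1 tabulates analysis-set counts and RAS exclusions by reason. If excluded AML subjects cannot be responders, a reader can rebuild the AML FAS rate. For ORR this is not assured, because of HI.

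**Conclusion.** The concern holds. Two endpoint sections of the SAP name only the set that the protocol reserves for sensitivity, and followed literally they omit the planned FAS estimates of best response rate and ORR. On the marrow reading, the AML RAS rate equals or exceeds the FAS rate; for ORR the same is expected apart from the rare HI case.

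The size is unknown and possibly negligible. It rests on an exclusion share the documents do not give and a term they do not define. Under the illustrative assumptions, one exclusion adds 0.5 percentage points at 52 subjects and 2.3 at 12, small against intervals more than 20 points wide. These are descriptive secondary rates, and the primary endpoint, boundaries and power do not change. The correction should be made because the contradiction is plain and cheap to remove.

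**What to change.** - In SAP 6.4.2.1 and 6.4.2.2, make the FAS the set for the estimate and its 90% interval, and repeat the analysis on the RAS as sensitivity. If the RAS is meant to lead, say so and justify the departure from the protocol.
- In SAP 4.2, define the qualifying post-baseline primary efficacy measurement, stating whether hematology alone is enough, and restore the RAS's sensitivity role.

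The cost is a few sentences and a few standard tables from data already collected. The reported secondary rates may be slightly less favourable.

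A separate, secondary point: SAP 6.4.2.3 to 6.4.2.5 give OS, EFS and duration of response in listings only, while protocol sections 9 and 9.4.2 plan Kaplan-Meier estimates. That change is logged and may be justified in the study report. I would still add the estimates by dose level, and by disease type in phase 2, alongside the listings.

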### 6.4.2.2 Objective Response Rate (ORR)

Objective Response Rate (ORR) is defined for MDS subjects as the number of subjects who achieve CR, BM CR, PR or HI at any of the postbaseline visits divided by the number of subjects in the analysis population. ORR is applicable for MDS subjects only.

The ORR will be estimated and its 90% confidence interval (CI) will be constructed by Clopper-Pearson method by dose level using the RAS.

### 6.4.2.3 Overall Survival (OS)

The date of last contact is the latest date the subject is known to be alive.

Subjects will be followed from first dose date until death or last contact.

For a subject who is not known to have died by the end of study follow-up, OS is censored at the date of last contact (date of last contact – first dose date + 1). OS will be presented in listing only.

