- If the posterior mean of the safety event rate is higher than 30% as indicated by Bayesian logistic model across disease types at a given dose level, then enrollment will be stopped in phase 2 at that dose level and at higher dose levels for that therapy.
- Additionally, if the posterior mean of the safety event rate is higher than 30% as indicated by Bayesian logistic model in a specific disease type at a dose level, enrollment of that dose level and any higher dose-level will be stopped for that disease type.

Statistical Methods

Sample Size Justification:

Phase 1 (Dose Escalation): The sample size for the dose escalation phase is not based on a statistical power calculation. The number of subjects enrolled will be dependent on the DLT incidence. The estimated number of subjects, a minimum of 6 evaluable and up to 18, should provide adequate information for the dose escalation and safety objectives of the study.

Phase 2 (Dose Expansion): The sample size in phase 2 is up to 104 subjects per dose level. Each dose level may enroll up to 52 R/R AML subjects and up to 52 R/R higher risk MDS subjects. The response rate is monitored using the BOP2 design. For AML, with assumption of the efficacious CRc rate is 30% and the inefficacious CRc rate is 15%, the statistical power would be approximately 0.83 while controlling the type I error rate at 0.10. For MDS, with assumption of the efficacious CR + BM CR + PR rate is 25% and the inefficacious CR + BM CR + PR rate is 12%, the statistical power would be approximately 0.83, while controlling the type I error rate at 0.10.

Efficacy:

For R/R AML: Response to treatment will be defined per modified Cheson criteria [Cheson et al, 2003].

For R/R higher risk MDS: Response to treatment will be defined per Cheson criteria [Cheson et al, 2006].

Response rates will be summarized using exact 90% confidence interval by dose level for phase 1 and by dose level and disease type for phase 2. Time to endpoints, including event free survival and overall survival, will be listed and summarized using Kaplan-Meier method.

Pharmacokinetics:

Summary statistics of pharmacokinetics may be tabulated. Exploratory analysis between pharmacokinetic parameter and clinical measures (e.g., efficacy or safety) may be performed.

Pharmacodynamics:

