3 STUDY OBJECTIVE(S) AND ENDPOINT(S)

The study objectives and endpoints for this study are provided in [Table 7](#).

Table 7 Study Objectives and Endpoints

Objective(s)	Endpoint(s)
Primary	
• To evaluate the safety and tolerability of ASP7517• To determine the RP2D and/or the MTD of ASP7517 (phase 1)• To evaluate the clinical response of ASP7517 
• Safety and tolerability as noted by: DLTs, AEs, SAEs, laboratory test results (serum, chemistry, hematology, coagulation, and urinalysis, pregnancy test) ECGs, vital signs, physical exams and ECOG performance status scores• CRc rate for subjects with R/R AML and (CR + BM CR + PR) rate for R/R higher risk MDS (phase 2)
Secondary	
• To evaluate other measures of anticancer activity of ASP7517 
• Duration of remission• EFS• OS• CR, best response (CRc + PR) and CRh rates for subjects with R/R AML• CR, HI and objective response (CR + BM CR + PR + HI) rates for subjects with R/R higher risk MDS
Exploratory	
• To evaluate potential genomic, proteomic and/or other biomarkers that may correlate with treatment outcome• To evaluate pharmacodynamic activities of ASP7517• To evaluate pharmacokinetics of ASP7517, which is determined by the kinetics of the cells 
• Exploratory biomarkers that may correlate with treatment outcome of ASP7517• Pharmacodynamic effects of ASP7517, such as changes in:
○ Cytokine expression and secretion (e.g., IFNg)○ WT1-specific T lymphocytes (e.g., cytotoxic T lymphocytes)○ Immune cell populations (NKT cells, NK cells, etc.)• Cellular DNA load and kinetic parameter estimates for ASP7517

AE: adverse event; AML: acute myeloid leukemia; BM: bone marrow; CR: complete remission; CRc: composite complete remission; CRh: complete remission with partial hematologic recovery; DLT: dose limiting toxicity; ECG: electrocardiogram; ECOG: Eastern Cooperative Oncology Group; EFS: event-free survival; IFNg: interferon gamma; HI: hematologic improvement; MDS: myelodysplastic syndrome; MTD: maximum tolerated dose; NK: natural killer; NKT: natural killer T; OS: overall survival; PR: partial remission; R/R: relapsed/refractory; RP2D: recommended phase 2 dose; SAE: serious adverse event; WT1: Wilms' tumor 1 protein.

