9 STATISTICAL METHODOLOGY

A statistical analysis plan (SAP) will be written to provide details of the analysis, along with specifications for tables, listings and figures to be produced. The SAP will be finalized before the database soft-lock at the latest. Changes from the planned analyses in the final SAP that impact the statistical analyses will be justified in the clinical study report (CSR).

In general, all data will be summarized by dose level and overall with descriptive statistics for continuous endpoints, and frequency and percentage for categorical endpoints, unless otherwise specified. Percentages by categories will be based on the number of subjects with no missing data (i.e., will add up to 100%). Kaplan-Meier estimates will be provided for time-to-event endpoints. Separate data displays will be produced for each phase of the study. For phase 1 dose escalation, all data will be summarized by dose level and overall, unless otherwise specified. For phase 2 dose expansion, all data will be summarized by disease group, dose level and overall, unless otherwise specified.

Baseline will be defined as the last nonmissing observation on or prior to first administration of IP, unless otherwise specified.

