- EFS is defined as the time from the date of first dose until the date of documented relapse, treatment failure or death from any cause within 30 days after the last dose of IP (whichever occurs first earliest of [relapse date, treatment failure date, death date] - first dose date + 1).
- Duration of remission for AML includes duration of CRc, duration of CR/CRh, duration of CRh, duration of CR, and duration of response (i.e., CRc + PR).
- Duration of remission for MDS includes duration of CR and duration of response (i.e., CR + BM CR + PR).

The distribution of OS, EFS and duration of remission will be estimated for each dose level using Kaplan-Meier methodology.

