### 5.1.9 Secondary Efficacy Endpoint: Duration of Response

Duration of response (DOR) for AML includes duration of CRc, duration of CR/CRh, duration of CRh, duration of CR, and duration of response (i.e., CRc + PR). DOR is defined as the time from the date of first response until the date of documented relapse.

Duration of response for MDS includes duration of CR and duration of response (i.e., CR + BM CR + PR). DOR is defined as the time from the date of first response date until the date of documented relapse.

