### 6.4.2.4 Event Free Survival (EFS)

For a subject with none of these events as relapse, treatment failure or death, EFS is censored at the date of last relapse-free disease assessment (last relapse-free disease assessment date – first dose date +1). Subject without post-treatment disease assessment will be censored at randomization date.

Treatment failure includes those subjects who discontinued the treatment due to “progressive disease” or “lack of efficacy” without a previous response of CR, CRp, CRI or PR.

EFS will be presented in listing only.

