### 6.4.2.5 Duration of Response

Duration of Response will be presented in listing only.

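### The protocol commits to Kaplan-Meier summaries of OS, EFS and duration of remission; the SAP gives listings only without explaining why, leaves DOR without censoring rules, and neither document plans a stand-alone HI rate

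*SAP*

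**What the plan says.** Protocol section 3 lists duration of remission, EFS and OS as secondary endpoints, together with "CR, HI and objective response (CR + BM CR + PR + HI) rates for subjects with R/R higher risk MDS".

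The protocol then commits to Kaplan-Meier three times:

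- Synopsis (1.1): "Time to endpoints, including event free survival and overall survival, will be listed and summarized using Kaplan-Meier method".
- Section 9: "Kaplan-Meier estimates will be provided for time-to-event endpoints".
- Section 9.4.2: "The distribution of OS, EFS and duration of remission will be estimated for each dose level using Kaplan-Meier methodology".

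The current SAP (version 3.0, 27 June 2023) plans something else:

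- 6.4.2.3: "OS will be presented in listing only".
- 6.4.2.4: "EFS will be presented in listing only".
- 6.4.2.5: "Duration of Response will be presented in listing only".

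The SAP revision history records both the removal of the Kaplan-Meier curve and the move to listings. On DOR, SAP 5.1.9 says for AML that "DOR is defined as the time from the date of first response until the date of documented relapse", with near-identical wording for MDS.

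**The concern.** The secondary objective is to evaluate other measures of anticancer activity. A listing that mixes event times and censored times gives no median, no survival proportion and no interval, so that objective would be reported without a summary for any of its three time-to-event endpoints. The two current documents also contradict each other, and nothing in either says which governs.

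Two further gaps compound this. DOR cannot be derived uniformly, even for a listing, if the plan does not say what happens to responders who never have a documented relapse. HI rate is named as an endpoint but has no analysis of its own.

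Finally, the study is open-label. Removing planned estimates in June 2023, in a study planned to start in about the third quarter of 2019, carries a risk of a selective-reporting criticism, which a stated reason would reduce.

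**Working it through.** No figure in the plan needs reproducing. The check is a comparison of texts, followed by a short precision calculation.

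**Kaplan-Meier.** The synopsis promises that times will be listed and also summarised, so a listing alone meets half of it. In the SAP, Kaplan-Meier appears only in the revision entry that removes it. No median, landmark proportion or interval for a time-to-event endpoint appears elsewhere. The log says that the curve will not be in the final outputs, which restates the decision. The rationale column speaks of clarifying PD and transfusion dependence, which has no bearing on dropping survival estimates.

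**DOR.** SAP Tables 2, 3 and 4 give event and censoring rules for OS, EFS and PFS. DOR has no such table. Its only endpoint is documented relapse, so a responder who dies without relapse, or is in remission at cutoff, has no defined value. For MDS, DOR includes BM CR, yet the relapse criteria in SAP 5.1.1 are headed for relapse after CR or PR.

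**EFS.** The definition differs between three places in the SAP:

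| Item | 5.1.8 | Table 3 | 6.4.2.4 |
|---|---|---|---|
| Death | Only within 30 days of last dose | No 30-day limit | No 30-day limit |
| Treatment-related event | Treatment failure, not defined there | Any premature discontinuation | Discontinuation for progression or lack of efficacy, without an earlier response |
| New anti-leukemic therapy | Not named | Event | Not named |
| No disease assessment | Not stated | Censored at first dose | Censored at randomization |

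The last row matters because SAP 2.3 calls for random allocation only when more than one dose level is open, so some subjects may have no randomization date.

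**HI rate.** SAP 5.1.1 defines HI, 5.1.5 ranks it in MDS best response, and 5.1.6 and 6.4.2.2 count it within ORR with a 90% Clopper-Pearson interval. SAP 5.1.2 to 5.1.9 contain no HI-rate endpoint, and 6.4.2 contains no HI-rate analysis. Protocol 9.4.2 also omits it from the rates it defines and gives intervals for. The rate cannot be recovered from ORR, which pools it with CR, BM CR and PR. Nor can it be recovered from best response: a subject with both BM CR and HI is ranked as BM CR.

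**Precision of a restored estimate.** Inputs: the cumulative BOP2 stage sizes of 12, 32 and 52 per disease type and dose level (protocol 9.4.1.3), and a 90% level to match the response-rate intervals. The assumptions are 50% survival at the landmark and little censoring; the documents give no survival figure for this purpose. Half-width = 1.645 × √(0.5 × 0.5 / n).

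- n = 52: 1.645 × √(0.25/52) = 0.114, about ±11 points.
- n = 32: 1.645 × √(0.25/32) = 0.145, about ±15 points.
- n = 12: 1.645 × √(0.25/12) = 0.237, about ±24 points.

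The smallest size is a real possibility. At the protocol's inefficacious rates, the chance of stopping at 12 is:

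- AML, at most 1 response at 15%: 0.85^12 + 12 × 0.15 × 0.85^11 = 0.142 + 0.301 = 0.44.
- MDS, no response at 12%: 0.88^12 = 0.22.

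**The case against.** The strongest reply is that the change is open and permitted. It is in the revision history, protocol section 9 allows the SAP to be finalized as late as database soft-lock, and changes are to be justified in the clinical study report. This stands in part: nothing was hidden. But a justification in the report would explain the omission without supplying an estimate, and the current documents would still disagree.

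A second reply is that a reader could compute Kaplan-Meier estimates from the listings. That is fair for OS, where Table 2 fixes event and censoring status. It does not hold for EFS until its definitions agree, or for DOR, which has no rules.

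A third is that these are uncontrolled secondary endpoints with no hypothesis, and that small cohorts make the estimates imprecise. Both statements are true. However, the SAP still gives 90% intervals for best response and ORR in the same cohorts, so small numbers alone do not explain the choice.

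Some stronger readings are tempting but go beyond the documents:

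- A reader might infer that the estimates were dropped because of what the data showed. Open-label design and ongoing review make access to data plausible, but neither document says what OS, EFS or DOR data had been seen. Only a risk of criticism can be claimed.
- A reader might infer that the SAP removed the HI analysis, or that HI is not analysed at all. HI is counted within ORR, the missing rate originates in protocol 9.4.2, and the synopsis's general statement on exact 90% intervals for response rates can be read to cover it.
- A reader might take ±11 points as the precision to expect. It is the best case of a full cohort of 52.

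**Conclusion.** The point holds as an unexplained and unreconciled departure. Three of three time-to-event secondary endpoints that the protocol says will be estimated by Kaplan-Meier have only a listing in the SAP. DOR lacks rules for responders without a documented relapse, and HI rate has no stand-alone analysis in either document. It does not extend to every secondary endpoint, since best response rate and ORR keep their intervals, and it does not touch the response-based efficacy decision.

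The textual conflict rests on no assumption. Only the precision range does, and it shows that restored estimates would be usable in a full cohort and coarse in one that stops early.

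**What to change.** 1. In SAP 6.4.2.3 to 6.4.2.5, restore Kaplan-Meier estimates for OS, EFS and DOR by disease type and dose level, with the median and a 90% interval where estimable. Keep the listings. The protocol promises only the estimated distribution; the median and interval are a recommended form of it.
2. Before estimating EFS, reconcile SAP 5.1.8, Table 3 and 6.4.2.4 on four items: the 30-day limit on deaths, any premature discontinuation versus treatment failure, new anti-leukemic therapy, and first dose date versus randomization date.
3. In SAP 5.1.9, add an event and censoring table for DOR that censors at the last relapse-free assessment and states how deaths without relapse are handled.
4. Add HI rate for MDS, with a 90% Clopper-Pearson interval, to protocol 9.4.2 and to the SAP.

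Amending the protocol to match the SAP and recording a real reason would remove the contradiction, but would still leave these endpoints without an estimate.

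The cost is a few tables, one DOR rule, the EFS reconciliation and a short protocol change. No new data are needed: protocol 8.2 already has survival followed every 3 months. The drawback is imprecise estimates where a cohort stops early. Label: cheap improvement.
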